This memorandum serves to notify the NCI and Southwest Oncology Group Statistical Center.

cc: PROTOCOL & INFORMATION OFFICE
[name].
[name], M.S.
[name]
[name]
[name] – CALGB
[name] - ECOG

Operations Office

[name] • San Antonio, TX 78245-3217 • [contact] • [contact] • <http://swog.org>

SOUTHWEST ONCOLOGY GROUP
PROTOCOL FAST FACT SHEET

THIS FORM HAS BEEN DESIGNED AS A RESOURCE ONLY AND IS NOT INTENDED FOR USE IN THE FULFILLMENT OF PATIENT REGISTRATION AND TREATMENT REQUIREMENTS

S0535

A Phase II Study of ATRA, Arsenic Trioxide and Gemtuzumab Ozogamicin in Patients with Previously Untreated High-Risk Acute Promyelocytic Leukemia

Drugs provided: **Gemtuzumab Ozogamicin**

Induction ATRA 45mg/m ² /day(in 2 doses, 22.5 mg/m ² every 12 hours PO, Day 1 to CR Gemtuzumab Ozogamicin 9 mg/m ² IV infusion over 2h, Day 1 only Arsenic Trioxide 0.15 mg/kg/d IV infusion over 2 hours 5 days/wk beginning on Day 10 and continuing until CR	
Consolidation Cycles 1 and 2 Arsenic Trioxide 0.15 mg/kg/day IV over 2 hours 5 days/week x 5 weeks, repeat after 2 weeks rest	
Consolidation Cycles 3 and 4 ATRA 45mg/m ² /day(in 2 doses, 22.5 mg/m ² every 12 hours PO, Days 1-7 Daunomycin 50 mg/m ² /day IV bolus or 1 hour infusion Days 1-3	
Consolidation Cycles 5 and 6 Gemtuzumab Ozogamicin 9 mg/m ² IV infusion over 2 hours Day 1 only	
Maintenance Chemotherapy ATRA 45/m ² /day(in 2 doses, 22.5 mg/m ² every 12 hours PO, Days 1-7 every 14 days 6MP 60mg/m ² /day PO daily for 1 year Methotrexate 20mg/m ² PO once per week for 1 year	
Eligibility	Ineligibility
Morphologically confirmed diagnosis of high risk acute promyelocytic leukemia (APL). Based on bone marrow examination performed within 14 days before registration. The WBC confirming high risk must be obtained within 14 days prior to registration.	Known PML-RAR α -negative by the RT-PCR assay.
Patient must have reached their 18 th birthday	Prior systemic therapy for acute leukemia (except ATRA for up to 3 days prior to registration). Administration of hydroxyurea, corticosteroids, and leukapheresis to control high cell counts prior to registration is permitted.

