1.2 Secondary Objective

To estimate the frequency and severity of toxicities of this regimen in this group of patients.

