3.4 Gemtuzumab ozogamicin (Mylotarg®) (NSC-720568) (IND-66,366)

a. DESCRIPTION

Antineoplastic Agent, Monoclonal Antibody.

Mechanism of Action: Antibody to CD33 antigen, which is expressed on leukemic blasts in 80% of patients with acute myeloid leukemia (AML), as well as normal myeloid cells. Binding results in internalization of the antibody-antigen complex. Following internalization, the calicheamicin derivative is released inside the myeloid cell. The calicheamicin derivative binds to DNA resulting in double strand breaks and cell death. Pluripotent stem cells and nonhematopoietic cells are not affected.

b. TOXICOLOGY

Human Toxicology: The following toxicities occurred in adults > 60 years of age. It is anticipated that these same toxicities are likely to occur (less frequently or to a lesser degree) in younger patients. Percentages estimated in adults > 60 years of age. > 10%: Cardiovascular: Peripheral edema (21%), hypertension (20%), hypotension (16%). Central nervous system: Chills (66%), fever (80%), headache (26%), pain (25%), dizziness (11%), insomnia (18%). Dermatologic: Rash (23%), petechiae (21%), ecchymosis (15%). Endocrine and metabolic: Hypokalemia (30%), hypokalemia. Gastrointestinal: Nausea (64%), vomiting (55%), diarrhea (38%), anorexia (31%), abdominal pain (29%), constipation (28%), stomatitis/mucositis (25%), abdominal distention (11%), dyspepsia (11%). Hematologic: Neutropenia (98%; median recovery 40.5 days), thrombocytopenia (99%; median

recovery 39 days); anemia (47%), bleeding (15%), lymphopenia. Hepatic: Hyperbilirubinemia (23%) increased LDH (18%), increased transaminases (9% to 17%). Local: Local reaction (25%). Neuromuscular & skeletal: Weakness (45%), back pain (18%). Respiratory: Dyspnea (36%), epistaxis (29%; severe 3%), cough (19%), pharyngitis (14%). Miscellaneous: Infection (28%), sepsis (24%), neutropenic fever (20%).

Percentages estimated in adults > 60 years of age. 1% to 10%: Cardiovascular: Tachycardia (10%). Central nervous system: Depression (10%), cerebral hemorrhage (2%), intracranial hemorrhage (2%). Endocrine and metabolic: Hypomagnesemia (4%), hyperglycemia (2%). Genitourinary: Hematuria (10%; severe 1%), vaginal hemorrhage (7%) Hematologic: Hemorrhage (8%), disseminated intravascular coagulation (DIC) (2%). Hepatic: Elevated PT. Respiratory: Rhinitis (10%), hypoxia (6%), pneumonia (10%), rhinitis (10%). Neuromuscular & skeletal: Arthralgia (10%).

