9.0 STUDY CALENDARS

REQUIRED STUDIES	PRE-STUDY	INDUCTION	CONSOLIDATION #1 through 2		CONSOLIDATION #3 through 4		CONSOLIDATION #5 through 6		MAINTENANCE		Follow Up
			Prior	During	Prior	During	Prior	During	Prior	During	
PHYSICAL											
History & Physical Exam	X	2X/week	X	X&	X	X α	X	X&	X	X&	X√
Height, Weight and BSA	X		X	X†	X	X†	X	X†	X	X&	X√
Performance Status (Zubrod)			X	X&	X	X α	X	X&	X	X&	X√
Toxicity Notation		2X/week	X		X		X		X	X&	X√
LABORATORY STUDIES											
CBC, Diff, Plts	X	2X/week	X	weekly	X	weekly	X	weekly	X	X&	X√
Pregnancy test	X										
Electrolytes (incl. Ca ⁺ and Mg ⁺⁺), creatinine *	X	2X/week	X	weekly	X	weekly	X	weekly	X	X&	
Bilirubin, AST, ALT, Alkaline phosphatase *	X	2X/week	X	weekly	X	weekly	X	weekly	X	X&	
Cholesterol, triglycerides *	X				X		X		X	X&	
PTT, PT, fibrinogen, FDP, D-dimer Δ *	X	2X/week									
BM Aspirate/Biopsy ⊖	X	X ψ	X		X				X	XΠ	X
Cytogenetics Σ	X	X ú									X¿
RT-PCR for PML-RARα Σ	X	X			X†				X		X¿
Lumbar Puncture (see Section 7.2b)			X								
X-RAYS AND SCANS											
Chest X-Ray %	X										
MUGA/ECHO					X#						
EKG \$	X	2X/week			X						
TREATMENT (See Section 7.0)											
Allopurinol/rasburicase		X									
ATRA		X f				X				X	
Daunomycin						X					
Arsenic trioxide		X		X							
6-mercaptopurine										X	
Methotrexate										X	
Gemtuzumab ozogamicin		X						X			

NOTE: Forms are found in Section 18.0. Forms submission guidelines are found in Section 14.0.

Click here to view [footnotes](#).

Footnotes:

- * Results of these tests do not determine eligibility but should be done prior to registration in accordance with good medical practice.
- & Monthly.
- √ After the patient is off treatment, the remaining of Months 3, 6, 9, 12, 18, 24 and 36 from the time of initial registration.
- Δ These tests should be done at pretreatment, twice weekly during induction until normal, and as clinically indicated thereafter.

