11.2 Molecular Response and Toxicity

With 70 eligible patients, the probabilities of molecular response and of any particular toxicity can be estimated to within at most $\pm 12\%$ (95% confidence interval). Any toxicity occurring with at least 5% probability is very likely to be observed in at least one patient (probability $\geq 97\%$).

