14.4 Data Submission Overview and Timepoints

- a. WITHIN 14 DAYS AFTER INITIAL REGISTRATION (STEP 1):

Submit the following:

S0535 Prestudy Form

Pathology Report

Pretreatment Cytogenetics Report (only required for patients from SWOG sites and other sites NOT affiliated with ECOG or CALGB)

Pretreatment RT-PCR Report (only required for patients from SWOG sites, CALGB sites and other sites NOT affiliated with ECOG)

See Section [15.0](#) for sample submission requirements.

- b. WITHIN 14 DAYS AFTER COMPLETING INDUCTION TREATMENT:

Submit the following:

S0535 Induction Treatment Summary Form

S0535 Adverse Event Summary Form

APL Disease Assessment Form

Off Treatment Notice (Please enter Step "1" on form.)

RT-PCR Report (only required for patients from SWOG sites, CALGB sites and other sites NOT affiliated with ECOG)

- c. WITHIN 14 DAYS AFTER COMPLETING EACH OF CONSOLIDATION CYCLES 1 AND 2 TREATMENT:

Submit the following:

S0535 Consolidation Cycles 1 and 2 Treatment Summary Form

S0535 Adverse Event Summary Form

- d. WITHIN 14 DAYS AFTER COMPLETING CONSOLIDATION CYCLE 2:

Submit the following:

APL Disease Assessment Form

RT-PCR Report (only required for patients from SWOG sites, CALGB sites and other sites NOT affiliated with ECOG)

- e. WITHIN 14 DAYS AFTER COMPLETING EACH OF CONSOLIDATION CYCLES 3 AND 4 TREATMENT:

Submit the following:

S0535 Consolidation Cycles 3 and 4 Treatment Summary Form

S0535 Adverse Event Summary Form

- f. WITHIN 14 DAYS AFTER COMPLETING EACH OF CONSOLIDATION CYCLES 5 AND 6 TREATMENT:

Submit the following:

S0535 Consolidation Cycles 5 and 6 Treatment Summary Form

S0535 Adverse Event Summary Form

- g. WITHIN 14 DAYS AFTER COMPLETING CONSOLIDATION CYCLE 6:

Submit the following:

APL Disease Assessment Form

- h. WITHIN 14 DAYS AFTER GOING OFF CONSOLIDATION TREATMENT:

Submit the following:

Off Treatment Notice (Please enter Step "2" on form.)

- i. WITHIN 14 DAYS AFTER REGISTRATION FOR MAINTENANCE THERAPY (Step 3):

Submit the following:

APL Disease Assessment Form

RT-PCR Report (only required for patients from SWOG sites, CALGB sites and other sites NOT affiliated with ECOG)

- j. EVERY 3 MONTHS WHILE ON MAINTENANCE THERAPY:
Submit the following:
S0535 Maintenance Treatment Summary Form
S0535 Adverse Event Summary Form
APL Disease Assessment Form
- k. WITHIN 14 DAYS AFTER GOING OFF MAINTENANCE TREATMENT:
Submit the following:
Off Treatment Notice (Please enter Step "3" on form.)

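### The AE Summary Form for Consolidation Cycles 5 and 6 falls due about Day 15, before expected count recovery and the next toxicity check, and no routine AE form is clearly assigned to the time after it

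*Combined protocol and SAP*

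**What the plan says.** Section 7.6d gives Consolidation Cycles 5 and 6 as one gemtuzumab infusion per cycle; the Fast Fact Sheet has "IV infusion over 2 hours Day 1 only". Section 14.4f asks for the Treatment Summary Form and the AE Summary Form "WITHIN 14 DAYS AFTER COMPLETING EACH OF CONSOLIDATION CYCLES 5 AND 6 TREATMENT".

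In the calendar (Section 9.0), the row "Toxicity Notation" is marked before each consolidation block, before maintenance, monthly during maintenance and at follow-up. It is blank in every consolidation During column. Blood counts and chemistry are weekly, and history and physical examination monthly, during Cycles 5 and 6.

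Section 3.4b lists "Neutropenia (98%; median recovery 40.5 days" and 39 days for platelets. It introduces these figures with "The following toxicities occurred in adults > 60 years of age" and expects the same toxicities to be "likely to occur (less frequently or to a lesser degree) in younger patients". Section 8.4b contemplates recovery to B1 taking up to 8 weeks from the start of Cycle 5, and uses liver abnormalities after Day 1 of Cycle 5 in decisions about Cycle 6.

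The secondary objective (Section 1.2) is: "To estimate the frequency and severity of toxicities of this regimen in this group of patients". Section 11.2 adds: "With 70 eligible patients, the probabilities of molecular response and of any particular toxicity can be estimated to within at most" 12 percentage points either way, with a probability of at least 97% of seeing one or more cases of a 5% toxicity.

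**The concern.** For Cycles 5 and 6 the last dose is also the first, so a deadline counted from the end of treatment arrives almost at once. A site that follows 14.4f as written files its routine AE form while many patients may still be cytopenic, and before the next toxicity notation on the calendar. An infection, bleed or liver abnormality that starts or worsens after filing has no routine form clearly assigned to it.

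Gemtuzumab is the investigational agent, and its toxicity within the regimen is what the secondary objective measures. The precision and detection figures in 11.2 take complete capture for granted. The primary outcomes, 3-year continuous CR and death within 6 weeks, are not touched.

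**Working it through.** **1. The plan's own figures (Section 11.2).** Largest 95% half-width with 70 patients: 1.96 × √(0.25/70) = 0.117, stated as 12%. Chance of at least one case of a 5% toxicity: 1 − 0.95^70 = 0.972, stated as at least 97%. Both reproduce.

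**2. When the form is due.** Inputs: infusion on Day 1 (7.6d) and 14 days (14.4f). Day 1 + 14 = Day 15.

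**3. Expected recovery.** Section 3.4b does not state the time origin; I assume days since the infusion.
- Neutrophils: 40.5 − 14 = 26.5 days after the due date.
- Platelets: 39 − 14 = 25 days after the due date.
- The 8 weeks in 8.4b: 56 − 14 = 42 days after the due date.

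If the medians are read as study-day numbers, the first two gaps are one day shorter. The 8-week figure does not rest on the over-60 data.

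**4. Earliest next step.** Cycle 6 (7.6b) and maintenance (7.7a) start no earlier than 2 weeks after count recovery. At the 3.4b neutrophil median this is 40.5 + 14 = 54.5 days after the infusion, or 54.5 − 14 = 40.5 days after the form was due. The notation before that step falls late in this interval.

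**5. Which AE form covers the interval?**
- After Cycle 5: the next AE Summary Form is the one for Cycle 6, due 14 days after the Cycle 6 infusion. Nothing says it picks up late Cycle 5 events.
- After Cycle 6, leaving consolidation (14.4h): Off Treatment Notice only.
- On registering for maintenance (14.4i): Disease Assessment Form and RT-PCR report only.
- During maintenance (14.4j): an AE Summary Form every 3 months, paired with the Maintenance Treatment Summary Form.
- Not entering maintenance (14.4m): Follow Up Form only. An AE Summary Form is required if the patient dies on protocol treatment (14.4n).

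**6. Expedited reports.** These cover serious events after gemtuzumab, including attributed ones beyond 30 days (Table 16.1). They exempt Grade 4 myelosuppression (16.1f) and use CTCAE 4.0, whereas routine toxicity uses 3.0 (8.1).

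**7. How 11.2 depends on capture (assumption only).** Let c be the share of affected patients whose event reaches the routine data. Detection of a 5% toxicity is 1 − (1 − 0.05c)^70: 0.972 at c = 1, 0.960 at 0.9, 0.931 at 0.75 and 0.830 at 0.5. The documents give no value of c, so this shows direction and not size.

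**The case against.** The strongest reply is that a submission deadline is not an observation window. Section 14.4 says when a form is due, not which period it covers, and nothing says later events are excluded or cannot be added. The AE Summary Form is not among the documents and may set its own period; the April 15, 2010 memorandum on idarubicin mentions a reporting period for the companion Cycles 3 and 4 treatment form. This stands: a reader might infer that toxicity after Day 15 goes unrecorded and that the estimate is biased low, and the documents do not show that. They also do not say how a later event enters the routine data.

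Completion of treatment could also be read to include recovery, since 14.4g asks for a disease assessment within 14 days of completing Cycle 6 although the next marrow is scheduled only before maintenance. But 14.4c, e and f, which carry the AE form, add the word treatment, while 14.4d and g do not. The plain reading is the end of dosing; at best sites would file at different times.

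Collection does continue. Weekly laboratory tests, the notation before the next step, maintenance AE forms and expedited reports would pick up part of what happens, and 8.4b obliges sites to follow liver tests and counts after Cycle 5. This shows that data exist at the site, not that they reach the routine AE dataset.

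The 40.5 days come from adults over 60, with less toxicity anticipated in younger patients, and they measure duration, while the objective is frequency and severity. A reader might take 14/40.5, about 35%, as the share of toxicity captured. That does not follow: slow recovery does not show that an event or a worst grade was missed, and the documents give no distribution of onset times.

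**Conclusion.** The point holds as a risk of under-recording in Consolidation Cycles 5 and 6. The routine AE form is due about Day 15. That is some 25 to 26.5 days before the median recovery in 3.4b and 42 days before the 8-week limit in 8.4b, and no routine AE form is clearly assigned from then to the next step. The gap is clearest after Cycle 6, and most of all in patients who do not enter maintenance.

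This rests on reading completion of treatment as the Day 1 infusion and, for the 3.4b gaps, on counting recovery from that infusion. How far frequency or worst grade would be understated cannot be derived from the documents.

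Two wider readings are not supported. A reader might extend the point to every gemtuzumab cycle, but the induction form follows completion of induction, where ATRA runs to CR for up to 90 days. A reader might extend it to Cycles 3 and 4, but the documents give no recovery time for those cycles. The change should be made because the affected item is the secondary objective and the remedy is cheap.

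**What to change.** - **14.4f:** have the Cycles 5 and 6 AE Summary Form record worst grade from Day 1 of the cycle through the start of the next cycle or maintenance. If neither starts, coverage runs through a fixed date no earlier than 8 weeks after Day 1, to match 8.4b. The form is due within 14 days after the end of coverage. Say how an event learned of after filing is added.
- Do not end coverage at B1 recovery. The next step starts at least 2 weeks after recovery, and liver events in that interval would be lost.
- **14.4h:** add the AE Summary Form for patients who leave consolidation without entering maintenance.
- **Section 9.0:** mark toxicity notation at the monthly visits already scheduled during Cycles 5 and 6.

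The cost is later receipt. At the 3.4b neutrophil median with the earliest permitted next step, the form would be due by 54.5 + 14 = 68.5 days after the infusion instead of 14, about 8 weeks later; slower recovery or a later start lengthens this. Expedited reporting continues unchanged meanwhile. No visit is added and treatment is not altered.

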- l. WITHIN 14 DAYS AFTER KNOWLEDGE OF A RELAPSE FROM COMPLETE REMISSION:
Submit the following:
A copy of the APL Disease Assessment Form documenting the date of and evidence for complete remission or relapse.
Submit Cytogenetics Report (only required for patients from SWOG sites and other sites NOT affiliated with ECOG or CALGB)
RT-PCR Report (only required from SWOG sites, CALGB sites and other sites not affiliated with ECOG)
- m. AFTER OFF TREATMENT: THE REMAINING OF MONTHS 3, 6, 9, 12, 18, 24 AND 36 FROM THE TIME OF INITIAL REGISTRATION:
Submit the following:
Follow Up Form.
- n. WITHIN 4 WEEKS AFTER KNOWLEDGE OF DEATH:
If death occurs while patient is on protocol treatment submit a copy of the Notice of Death, the **S0535** Adverse Event Summary Form and the Treatment Summary Form that corresponds with the Step and Cycle of treatment the patient was receiving at the time of death.
If the death occurs after off treatment submit a final Southwest Oncology Group Follow Up Form. Also submit a copy of the Notice of Death.

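### Section 14.4 assigns no toxicity form to the interval before a non-fatal early stop of maintenance, so maintenance toxicity data may be incomplete

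*Combined protocol and SAP*

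**What the plan says.** The secondary objective (1.2) is "To estimate the frequency and severity of toxicities of this regimen in this group of patients". The routine source for it is the S0535 Adverse Event Summary Form, whose due dates are set in 14.4:

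- **Induction (14.4b).** The form is due "WITHIN 14 DAYS AFTER COMPLETING INDUCTION TREATMENT", together with the induction treatment summary and the Step 1 Off Treatment Notice.
- **Consolidation (14.4c, e, f).** The form is due after each cycle, for example "WITHIN 14 DAYS AFTER COMPLETING EACH OF CONSOLIDATION CYCLES 1 AND 2 TREATMENT". The off-consolidation item (14.4h), "WITHIN 14 DAYS AFTER GOING OFF CONSOLIDATION TREATMENT", lists only the Step 2 Off Treatment Notice.
- **Maintenance (14.4j, k).** The toxicity and treatment summary forms are due "EVERY 3 MONTHS WHILE ON MAINTENANCE THERAPY". The item "WITHIN 14 DAYS AFTER GOING OFF MAINTENANCE TREATMENT" lists only the Step 3 Off Treatment Notice.
- **Death (14.4n).** "If death occurs while patient is on protocol treatment submit a copy of the Notice of Death"; the same sentence also requires the Adverse Event Summary Form and the Treatment Summary Form for the current step and cycle.

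Section 7.12 requires the reason for stopping to be given on the Off Treatment Notice. Section 7.11d makes unacceptable toxicity a ground for removal. The study calendar (9.0) has toxicity noted monthly during maintenance.

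**The concern.** The maintenance forms depend on the patient still being on therapy, and the off-maintenance item does not close the interval in progress. When a patient stops between two scheduled forms, the next one no longer falls due. The uncovered interval is not a random sample of time on treatment: for a patient removed under 7.11d it is the interval that ends in the toxicity. At stake is whether the frequency and severity of toxicity, which is the secondary objective and the content of the six-monthly toxicity reports in 11.4, are complete for maintenance.

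**Working it through.** **1. Time without a form.** Take the three-month intervals as running from the start of maintenance (an assumption; 14.4j names no origin) and let a patient stop non-fatally at month *t*. The time since the last form is *t* − 3 × floor(*t*/3).

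- Stop at month 5: 5 − 3 = 2 months uncovered.
- Stop at month 2: 2 − 0 = 2 months uncovered, and no maintenance toxicity form exists at all.
- Finish the one-year course of 6-MP and methotrexate: 12 − 12 = 0.

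The gap therefore runs from 0 to just under 3 months and concerns early stops only.

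**2. The plan's own closing rules.** Induction closes with a toxicity form and the notice together (14.4b). Death on treatment closes with a toxicity form and a treatment summary (14.4n). A non-fatal stop of maintenance closes with the notice alone (14.4k). The plan thus recognises that an interrupted interval needs closing forms, but in maintenance it requires them only for death.

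**3. What other channels carry.**

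- *Off Treatment Notice:* the reason for stopping. Nothing in the documents makes it a graded list of all toxicities.
- *Expedited reporting under the investigational rules:* Appendix 18.1 says these rules govern once the investigational agent has been started, and gemtuzumab is given in induction. Table 16.1 takes serious events. More than 30 days after the last gemtuzumab dose, its footnote also requires attribution. Section 16.1f exempts Grade 4 myelosuppression.
- *Expedited reporting under the commercial rules:* 16.1g sends the maintenance drugs to Table 16.2, which takes attributed unexpected Grade 4 events and Grade 5 events. It has no Grade 3 column, and expected Grade 4 is blank.
- *Grading:* expedited reports use CTCAE 4.0 and routine toxicity uses 3.0 (8.1, 10.8), so the two streams cannot simply be pooled.

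Under either set of rules, non-serious Grade 3 events are not captured. Grade 4 myelosuppression is exempt under the first and, being expected, not taken by the second. Section 3.5 names myelosuppression as the dose-limiting toxicity of 6-MP.

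**4. The plan's figures.** Section 11.2 gives a 95% half-width of at most 12 points and at least a 97% chance of seeing a toxicity with a true rate of 5%, both with 70 patients.

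- Half-width: 1.96 × √(0.25/70) = 0.117, or 11.7 points.
- Detection: 1 − 0.95^70 = 0.972.

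Both reproduce, and both presuppose that every toxicity that occurs is recorded. On that denominator, one affected patient with no record lowers a rate by 1/70 = 1.4 points. The documents give neither the number of early stops nor the share with an unrecorded toxicity, so the calculation cannot go further.

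**5. Primary endpoints.** Six-week death and three-year continuous remission (11.1) are not derived from the maintenance toxicity form. The Section 11 figures are unchanged.

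**The case against.** Several points on the other side have force.

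- *The toxicity that ended treatment is not simply lost.* A reader might infer that it is. Section 7.12 sends the stopping reason to the data center within 14 days on the notice. What may be missing is the full CTCAE 3.0 grading for the last interval. This stands and limits the point.
- *Consolidation.* A reader might infer the same gap there, because the forms follow *completing* a cycle. The wording does not settle it. Item 14.4b uses the same word and is the only listed trigger for the Step 1 notice, which 7.12 requires for every discontinuation. The word can therefore mean the end of treatment however it came about. Section 14.1 also requires data for all registered patients. Cycles 5 and 6 are single-day infusions, so a mid-cycle stop is hardly possible. This is an ambiguity, not a demonstrated gap.
- *Serious events have a route.* Table 16.1, through Appendix 18.1, takes attributed serious Grade 3 to 5 events even late in maintenance. This stands in part; step 3 shows what remains outside.
- *Earlier records.* Section 8.5 often handles 6-MP and methotrexate toxicity by holding and resuming at a lower dose. Many patients who eventually stop would already have the toxicity on a three-monthly form, and a worst-grade rate would not change for them. This stands, and is one reason no size can be given.
- *Forms not seen.* The forms are not reproduced in the text. The Adverse Event Summary Form may carry its own instruction for a final partial period, and the Follow Up Form due after treatment (14.4m) may collect toxicity. Nothing here rests on the content of either. The schedule itself should still state what is due.

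**Conclusion.** The point holds for maintenance. Followed as written, 14.4j and 14.4k leave up to about three months before a non-fatal early stop with no assigned Adverse Event Summary Form or Maintenance Treatment Summary Form. Non-serious Grade 3 events and Grade 4 myelosuppression in that interval may go unrecorded. Because a missing record can leave a per-patient toxicity rate unchanged or lower it, but not raise it, any error is most likely an understatement.

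The stronger statement that the toxicity rates are biased low by a known or material amount is not supported. The documents give no rate of early stopping and no share of unrecorded events. The conclusion assumes that sites follow the schedule literally and that the forms carry no instruction that closes the interval. It affects the secondary objective and the routine toxicity reports. It does not affect the primary endpoints or the early-stopping rule.

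**What to change.** In 14.4k, add a final S0535 Maintenance Treatment Summary Form and S0535 Adverse Event Summary Form covering the time since the last such form (or since the start of maintenance if none has been filed), submitted with the Off Treatment Notice. This extends to all early stops what 14.4n requires for deaths.

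As a clarification only, write *completing or discontinuing* in 14.4b, c, e and f, so that a course or cycle stopped early clearly triggers its forms.

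The cost is a line in each item and one existing set of forms per early stop, filled from the monthly toxicity notes already in the chart. No visit, test or treatment rule changes. For patients already off maintenance, the equivalent is a site query for the missing interval. Failing that, the toxicity report should state that the last interval before an early stop may be incomplete.
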